8.3.5 Surgical Prophylaxis

Efficacy of Octafibrin in surgical prophylaxis will be assessed intra-operatively (at the end of surgery = after last suture) by the surgeon and post-operatively by the haematologist using two 4-point efficacy scales. In the event that any intra- or post-operative endpoint data differ between the Investigator's assessment and the adjudicated assessment by the IDMEAC, the primary endpoint will be that based on the adjudicated assessments. The efficacy of Octafibrin in surgical prophylaxis will be evaluated by descriptive statistics based on an overall assessment.

In the documentation of the adjudication process for the assessment of surgical prophylaxis the DMEAC will explicitly identify any subjects for whom they considered there to be "unexpected blood loss due to surgical complications" and if that consideration altered the 4-point assessment of surgical prophylaxis. This information will be analyzed both including (as a sensitivity analysis) and excluding unexpected blood loss if it occurs.

9 SAFETY ANALYSES

AEs and SAEs will be coded by latest version 17 or higher of MedDRA body system and preferred term, and tabulated by indicating number and percentage of subjects and number of events. Number and percentage of subjects who experience any Adverse Drug Reaction (ADR) will be summarized.

AEs will be collected and evaluated for relation to test article, seriousness, intensity, frequency, measures taken and outcome.

Descriptive statistics and subject listing will be presented for concomitant medications.

The analysis of safety will be based on the safety population.

All AEs occurring after initiation of study treatments (including events likely to be related to the underlying disease, or a concomitant illness or medication or clinical significant abnormalities in laboratory parameters or vital signs) will be displayed in summary tables and listings.

Treatment emergent AEs will be those occurring during infusion or in the 45-day observation period after the first infusion. ADRs will be classified by the Sponsor as either expected or unexpected

FORMA-02	JSS Medical Research - Data Management		
Statistical Analysis Plan			
Form Number: MNI-DM-BIS-01 v 6.0-T1	Current Version Number: 2.0	Previous Version Number: 1.1 9-April-2015	Date: 11-July-2016

Incidences of AEs will be given as numbers and percentages of subjects with:

- Any AE.
- Any SAE.
- Any AE probably or possibly related to the IMP.
- Any AE temporally related (within 24 hours after end of infusion) to the IMP.
- Any severe AE.
- Any withdrawal due to AE.
- Any AE by Medical Dictionary for Regulatory Activities (MedDRA) preferred term (descending frequency).
- Any AE temporally related (within 24 hours after end of infusion) by MedDRA preferred term (descending frequency).
- Any AE by MedDRA system organ class (SOC).
- Any AE temporally related (within 24 hours after end of infusion) by MedDRA SOC.

Summary tables for AEs will be given by SOC and preferred term. Additionally, AEs will be summarized by severity and relationship to the IMP.

The MedDRA coded terms and the corresponding original (verbatim) terms used by the investigator will be listed.

For laboratory variables (analyses of haematology, biochemistry, and thrombogenicity), the mean, standard deviation, median, and range will be presented. Laboratory variables will also be presented graphically. Intra-individual changes between baseline and the respective post-baseline time points will be analyzed using shift tables and graphical presentations. Virus safety variables and physical examination will be evaluated via frequency tables.

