7.4 Safety Assessments

Any of the following drug safety information shall be collected:

- All AEs occurring between the start of the first Octafibrin infusion and the end of each 30day observation and follow-up period for on-demand treatment or until the Last Post-Operative Day in surgeries will be recorded.
- All SAEs occurring after the first *Octafibrin* infusion will be documented and reported for a patient throughout the duration of the patient's participation in the study or as required to meet local regulations (definitions and reporting requirements, see Section 7.4.1).
- Post study related safety reports, pregnancies, drug overdose, interaction, abuse, misuse, or medication error (see Section 7.7).

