7.4.1.2 Collection of AEs

The condition of the subject will be monitored throughout each **30-day observation and follow-up period** for on-demand treatment or each **surgical observation period** for surgical interventions. At each visit, whether scheduled or unscheduled, AEs will be elicited using a standard non-leading question such as 'How have you been since the last visit?'

Only AEs or ADRs which occur during any 30-day observation and follow-up period for ondemand treatment or any surgical observation period for surgical interventions will be recorded in detail on the appropriate pages of the CRF. If the subject reports several signs or symptoms which represent a single syndrome or diagnosis, the latter should be recorded in the CRF.

The investigator responsible will grade the severity of all AEs or ADRs (mild, moderate, or severe; see Section 7.4.1.3), the seriousness (non-serious or serious; see Section 7.5), and causality (see Section 7.4.1.4). The Sponsor is responsible to assess the expectedness of each ADR (expected or unexpected; see Section 7.4.1.5).

In the event of clinically significant abnormal laboratory findings, the tests will be repeated and followed up until they have returned to normal and/or an adequate explanation is available.

Diseases, signs and symptoms and/or laboratory abnormalities already existing before the first administration of IMP are not considered as AEs when observed at a later stage unless they represent an exacerbation in intensity or frequency (worsening).

The investigator responsible should always provide detailed information concerning any abnormalities and the nature of, and reasons for any necessary action(s), as well as any other

observations or comments, which are useful for the interpretation and understanding of the subjects' AEs or ADRs.

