7.5 Serious Adverse Events

All reported SAEs occurring after the first administration of IMP in the study will be documented and reported for a patient throughout the duration of the patient's participation in the study. This will be designated as occurring in either an "active period" (i.e., during the treatment observation and follow-up period) or an "inactive period" between treatment events (i.e., bleeding or surgery).

All related concomitant medications will also be collected for these events.

No SAEs will be collected between screening and the first treatment unless required by local regulations.

An SAE is any untoward medical occurrence that at any dose:

- Results in death.
- Is life-threatening.
- Requires hospitalisation or prolongation of existing hospitalisation.
- Results in persistent or significant disability/incapacity.
- Is a congenital anomaly/birth defect.
- Is another important medical event.

NOTE: The term 'life-threatening' refers to an event in which the subject was — in the view of the reporting investigator — at immediate risk of death at the time of the event; it does not refer to an event which hypothetically might have caused death if it were more severe.

In other situations, medical judgement should be exercised in deciding whether an AE/ADR is serious: Important AEs/ADRs that are not immediately life-threatening or do not result in death or hospitalisation but may jeopardise the subject or may require intervention to prevent one of the other outcomes listed in the definitions above, should also be considered serious.

In addition, although not classified under the seriousness criteria, all suspected transmissions of an infectious agent should be reported as SAE. A suspected virus transmission means that virus antigen has been detected in the subject. A passive transmission of antibodies alone does not constitute a suspected virus transmission.

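### SAP section 9 pools SAEs collected from first infusion to the end of participation with other AEs collected only in treatment-episode windows, and omits the protocol's active/inactive split of SAEs

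*SAP*

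**What the plan says.** Protocol 7.4 has SAEs after the first infusion documented "for a patient throughout the duration of the patient's participation in the study or as required to meet local regulations". Protocol 7.5 repeats this ("All reported SAEs occurring after the first administration of IMP in the study will be documented and reported for a patient throughout the duration" of participation) and sets the starting point: "No SAEs will be collected between screening and the first treatment unless required by local regulations". It then has each SAE designated as belonging to an active period (treatment observation and follow-up) or to an inactive period between treated bleeds or surgeries.

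Other AEs have a narrower window. Protocol 7.4.1.2 has recorded in detail "Only AEs or ADRs which occur during any 30-day observation and follow-up period for ondemand treatment or any surgical observation period" for surgical interventions. Under Protocol 6.1.3.3 the surgical period closes on post-operative day 3 (minor) or 7 (major), or on the day of the last post-operative infusion if that is later.

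SAP section 9 puts "All AEs occurring after initiation of study treatments" into summary tables and listings. It then lists incidence rows as numbers and percentages of subjects: any AE, any SAE, any severe AE, related AEs, AEs within 24 hours of infusion, withdrawals, and rows by preferred term and system organ class. The active/inactive designation does not appear. Protocol 9.4.2.5 lists the same rows and omits it too. Between the display sentence and the list, the SAP defines treatment-emergent AEs as those during infusion or in the 45 days after the first infusion, but does not say which rows use that definition.

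**The concern.** Between treated episodes only serious events can enter the safety tables. The any-SAE row can therefore grow with time since first infusion, while the non-serious count grows only with the number of treated episodes. The any-AE, any-severe-AE and MedDRA rows inherit the mixture, because outside the windows they can gain serious events only.

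The trial has no control arm to show the background, so the all-causality SAE percentage will be read as a main safety figure. If it combines events near an infusion with events long after one, a reader cannot tell how much reflects exposure and how much reflects length of stay. Nor can the serious share of all AEs be interpreted. The protocol created a label that separates the two, and the analysis plan does not use it.

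**Working it through.** The plan states no figure on this point, so there is nothing to reproduce. The check compares collection windows with table rows; the arithmetic after that is illustrative.

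**Step 1: collection windows after the first infusion**

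| Event type | Collected during | Source |
|---|---|---|
| SAE | First infusion to end of participation | Protocol 7.4, 7.5 |
| Non-serious AE, bleed | 30 days per treated episode (Day 30 visit has a 1-week tolerance) | Protocol 6.1.2, 7.4.1.2 |
| Non-serious AE, surgery | Day 1 plus 3 or 7 post-operative days, so at least 4 or 8 days; longer if infusions continue | Protocol 6.1.3.3, 7.4.1.2 |

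Patients may stay until the 24th patient has a documented bleed (Protocol 3.2), and the study should finish within 5 years (Protocol 6.2.1). Five years is thus a ceiling, approached only by a subject infused near the start.

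**Step 2: time limits in SAP section 9**

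The only rows with a stated time limit are those for events within 24 hours after the end of an infusion. The 45-day definition is attached to no row, equals neither window in Step 1, and does not say how later episodes count.

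**Step 3: share of SAE collection time inside the common window**

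Share = window days / days from first infusion to end of stay. The stays are assumed.

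- One bleed: 30/183 = 16.4% (6 months); 30/365 = 8.2% (1 year); 30/730 = 4.1% (2 years); 30/1826 = 1.6% (5 years).
- Three separate bleeds in 1 year: 90/365 = 24.7%.
- Surgery only, 1 year: 4/365 = 1.1% (minor); 8/365 = 2.2% (major).

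**Step 4: illustrative effect on the any-SAE row**

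P(at least one SAE) = 1 − exp(−rate × days/365.25), for a constant background rate unrelated to the product. The documents give no SAE rate, so every rate here is assumed.

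| Assumed rate per patient-year | One 30-day window | 1 year | 2 years |
|---|---|---|---|
| 0.05 | 0.4% | 4.9% | 9.5% |
| 0.1 | 0.8% | 9.5% | 18.1% |
| 0.2 | 1.6% | 18.1% | 32.9% |
| 0.4 | 3.2% | 32.9% | 55.0% |

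At 0.1 per patient-year and 24 subjects, these are about 24 × 0.008 = 0.2, 24 × 0.095 = 2.3 and 24 × 0.181 = 4.3 subjects. With three bleed windows in the year the in-window figure is 1 − exp(−0.1 × 90/365.25) = 2.4%, still against 9.5% for the whole year. Repeated episodes narrow the gap but do not close it.

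**The case against.** The strongest reply is that a row counting every post-treatment SAE is the cautious choice for a plasma-derived product. Protocol 1.5 names thromboembolism and infection as risks, and Protocol 7.5 requires suspected transmission of an infectious agent to be reported as an SAE. After minor surgery the active window can close on post-operative day 3. Restricting every incidence and MedDRA row to active-period onset could therefore remove a delayed event from the headline tables. This stands: the total row should be kept and the split added beside it.

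Second, attribution is partly covered. SAP section 9 also has rows for related AEs and for AEs within 24 hours of infusion, an ADR summary, and tables by relationship. SAP section 11 lists all CRF data, so the designation would appear there if it is a CRF field. Safety analysis is descriptive (Protocol 9.2), and with about 24 subjects each SAE can be read individually. This lowers the stakes, but it does not make the AE and SAE percentages comparable.

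Third, a programmer might apply the 45-day definition to the whole list, which would drop many inactive-period SAEs. The text neither requires nor excludes that, and this ambiguity is itself part of the problem.

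Fourth, the flow charts in both documents run the AE row to the Study Completion Visit. The explicit text of Protocol 7.4 and 7.4.1.2 limits recording to the windows, and I have followed it. The SAP refers to protocol Version 7.0, whereas the protocol supplied is Version 6.0, so whether these sections are unchanged cannot be checked.

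**Conclusion.** The point holds as a matter of table design. The all-causality SAE percentage in SAP section 9 depends on time in the study as well as on exposure, and it is not on the same footing as the non-serious AE percentage. The designation in Protocol 7.5 that would separate the two is unused, and the treatment-emergent definition is attached to no row.

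A reader might infer more than the documents support:

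- That SAEs are collected over the whole stay. Collection starts at the first infusion; events between screening and first treatment are excluded unless local rules require them.
- That months off product are being set against a few days on it. That fits surgery at its minimum of 4 or 8 days. A bleed window is 30 days and may recur.
- That the product's SAE rate will be inflated by a known amount. The documents give neither an SAE rate nor individual lengths of stay. The contrast of 0.8% with 9.5% and 18% rests on an assumed 0.1 SAE per patient-year, one treated bleed, and stays of 1 and 2 years.

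The primary efficacy analysis is unaffected. This is an inexpensive improvement in how safety is reported.

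**What to change.** In SAP section 9:

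1. Keep the total post-treatment SAE row, and add columns or rows for active-period SAEs, inactive-period SAEs and the total, using the Protocol 7.5 designation.
2. Present AE and SAE incidence and the system organ class and preferred term tables also for the common active window, so that serious and non-serious events are counted over the same time.
3. List inactive-period SAEs with time since last infusion, so that delayed events stay visible.
4. State which rows are restricted to treatment-emergent events.
5. Confirm that the designation remains in protocol Version 7.0 and is captured on the CRF.

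The cost is a short SAP edit and one or two extra tables. If the designation is captured as Protocol 7.5 requires, no new data are needed. Because the total row stays, no event leaves the headline tables.

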5.5 Preparation and Method of Administration

5.5.1 Preparation

Each vial of *Octafibrin* will be reconstituted with 50 mL WFI. The solvent (i.e., WFI) and the concentrate in the closed vials must be warmed up to room temperature. Room temperature must be maintained during reconstitution. *Octafibrin* dissolves at room temperature to an almost colourless and slightly opalescent solution within 30 minutes. If the solution is cloudy or contains particulates, it should not be used. The solution should not be frozen.

Octafibrin should be administered immediately after reconstitution at a rate not exceeding 5 mL per minute. Octafibrin should not be mixed with other medicinal products or intravenous solutions.

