3.1.2 Secondary Objectives

- To show an association between the overall clinical assessment of haemostatic efficacy and the surrogate endpoint 'clot strength' or 'clot firmness' (referred to as 'Maximum Clot Firmness' [MCF]) that was used as a surrogate endpoint for haemostatic efficacy and determined via Thromboelastography (TEG) in the pivotal Pharmacokinetic (PK) study FORMA-01. Therefore, MCF as surrogate efficacy parameter will be determined before first infusion and 1 hour after the end of first and last infusion.
- To achieve peak target plasma fibrinogen level of 100 mg/dL in minor bleeds and 150 mg/dL for major bleeds 1 hour post-infusion.
- To determine the response to Octafibrin based on incremental in vivo recovery (IVR).
- To demonstrate the efficacy of Octafibrin in preventing bleeding during and after surgery.
- To assess the safety of Octafibrin in subjects with congenital fibrinogen deficiency, including immunogenicity, thromboembolic complications, and early signs of allergic or hypersensitivity reactions.

FORMA-02	JSS Medical Research - Data Management	 JSS <small>RESPONSIVE RELIABLE RESULTS</small>	
Statistical Analysis Plan			
Form Number: MNI-DM-BIS-01 v 6.0-T1	Current Version Number: 2.0	Previous Version Number: 1.1 9-April-2015	Date:11-July-2016

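### The temporally related AE outputs open their 24-hour window at the end of the infusion, so an event starting during an infusion is left out of them unless an earlier infusion's window happens to cover it

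*SAP*

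**What the plan says.** SAP section 9 lists the AE incidences to be reported. Three of them concern temporally related events. The overall line is "Any AE temporally related (within 24 hours after end of infusion) to the IMP" and the organ-class line is "Any AE temporally related (within 24 hours after end of infusion) by MedDRA SOC"; the preferred-term line carries the same bracket. Protocol v6.0 section 9.4.2.5 gives the same three lines with the same window, so it does not repair the SAP. Neither document extends the window to onset during the infusion.

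Four other statements bear on the point:

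- The same SAP section defines a different class of event as follows: "Treatment emergent AEs will be those occurring during infusion or in the 45-day observation period after the first infusion".
- The general AE tables and listings in that section cover "All AEs occurring after initiation of study treatments".
- Protocol section 7.4 sets the collection period for on-demand treatment as "All AEs occurring between the start of the first Octafibrin infusion and the end of each" 30-day follow-up period; for surgery it runs to the last post-operative day.
- The safety objective in SAP section 3.1.2 is stated as "including immunogenicity, thromboembolic complications, and early signs of allergic or hypersensitivity reactions".

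**The concern.** A window that begins when the infusion ends does not contain the infusion. If an AE is timed by its onset, which the bracket does not spell out but which is the usual convention, an event that begins between start and end of an infusion precedes the window. A programmer following the text would not flag it.

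The treatment-emergent definition in the same section makes this reading more likely. There the SAP names the infusion expressly; in the temporally related bracket it does not.

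At stake is the accuracy of three descriptive safety outputs. Among the outputs listed in SAP section 9, these are the ones that pick out events close to an infusion by timing rather than by the investigator's causality judgement, and the study is open-label. The section lists no separate hypersensitivity table, and protocol section 1.5 puts hypersensitivity first among the expected reactions. An incidence labelled temporally related that leaves out the infusion itself would be understated for such reactions, and a reader of the table would have no way of knowing.

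**Working it through.** The plan states no figure that depends on this window, so there is nothing to reproduce. Three things can be checked: how long the uncovered interval is, when an earlier infusion covers it, and what one omission does to an incidence.

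**1. Length of the uncovered interval**

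Inputs from the protocol:

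- Concentration: 20 mg fibrinogen per mL (section 5.1, Table 1).
- Rate: "at a rate not exceeding 5 mL per minute" (section 5.5.1). The maximum delivery is therefore 20 × 5 = 100 mg/min.
- Recommended targets: 100 mg/dL (minor) and 150 mg/dL (major) (sections 5.4.2 and 5.4.3).
- Dose formula (section 5.4.1): dose in mg/kg = (target − measured level) / median response.

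Assumptions: body weight 70 kg, measured level 0, and a response of 1.5 to 2.0 (mg/dL)/(mg/kg). The protocol takes the response from an interim analysis of FORMA-01 and prints no value.

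Minimum infusion time (min) = (target / response) × weight / 100.

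| Target (mg/dL) | Assumed response | Dose at 70 kg (mg) | Volume (mL) | Minimum time (min) |
|---|---|---|---|---|
| 100 | 2.0 | 3,500 | 175 | 35.0 |
| 100 | 1.5 | 4,667 | 233 | 46.7 |
| 150 | 2.0 | 5,250 | 262.5 | 52.5 |
| 150 | 1.5 | 7,000 | 350 | 70.0 |

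With a response of 1.0 to 2.5 and weights of 40 to 90 kg, the extremes are (100 / 2.5) × 40 / 100 = 16 min and (150 / 1.0) × 90 / 100 = 135 min. A slower rate lengthens every figure. A measured level above 0, as before many repeat infusions, shortens it.

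**2. Cover from an earlier infusion**

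Let two infusions each last D hours, with their starts g hours apart. The first infusion's window closes at D + 24 hours; the second infusion runs from g to g + D.

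- If g ≤ 24, the second infusion lies wholly inside the first one's window, and an onset during it is counted.
- If g is between 24 and 24 + D, the cover is partial. At g = 24.25 it is 50% for D = 0.5 and 75% for D = 1.
- If g ≥ 24 + D, there is no cover. At g = 26 or 48 it is 0% for both values of D.

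Levels are checked daily and infusions repeated as needed, so some repeat infusions would be covered and others not, depending on clock times. The first infusion of an episode has no predecessor in that episode and no cover.

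**3. Effect on an incidence**

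The planned minimum is 24 subjects with a treated bleed. One omitted subject is 1/24 = 4.2 percentage points. The safety population is everyone with at least one infusion, so the denominator may be larger and the share smaller. In the overall line, a subject drops out only if no other AE of theirs falls in a window; in the preferred-term and organ-class tables the same holds within that term or class.

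**The case against.** The strongest reply is that the safety reporting does not depend on these three outputs. AEs are collected from the start of the first infusion. An event during an infusion still enters the any-AE, serious, severe and related counts, the ADR count, the full preferred-term and organ-class tables, and the listings. The protocol's causality scale (section 7.4.1.4) itself takes temporal sequence from administration into account, so an infusion reaction can be shown among the related events. All of this stands, and it limits the consequence.

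A second reply is that the bracket may be shorthand for the outer limit of a window that starts with the infusion. That is possible, but nothing in either document says so, and the contrast with the treatment-emergent wording points the other way. If two programmers can obtain different counts from the same text, it needs to be fixed under either reading.

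A third reply is that nothing shows how many events would be affected. This also stands. The documents give no expected rate of AEs during infusion, so the understatement can be bounded per subject but not predicted.

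A reader might go further and infer that infusion reactions would disappear from the study's safety results, that every onset during an infusion is lost from these tables, or that the tables exist specifically to show hypersensitivity. The documents support none of these. The events remain in the other outputs, onsets during closely spaced repeat infusions are counted, and neither document states what the tables are for. The link to hypersensitivity comes only from the safety objective.

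**Conclusion.** The definition is wrong as written, with a limited consequence. Followed literally, it removes onsets during an infusion from all three temporally related outputs unless the 24 hours after an earlier infusion cover them, and it always removes onsets during the first infusion of an episode. The affected incidences can only be too low, never too high.

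The interval left out is at least about 35 to 47 minutes for the lower target and 52 to 70 minutes for the higher one. This rests on 70 kg, a starting level of 0, the maximum rate, and an assumed response of 1.5 to 2.0. One omitted subject is worth about 4 percentage points at the minimum of 24.

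No data are lost, and no efficacy result or hypothesis test is touched. It should be corrected because the safety objective names early allergic reactions and the correction costs almost nothing.

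**What to change.** In SAP section 9, define a temporally related AE as one with onset from the start of any infusion to 24 hours after the end of that same infusion, and apply this to all three outputs. State that timing refers to onset.

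Align the protocol's list (section 9.4.2.5 in v6.0). The SAP is written to protocol v7.0, which is not among the documents reviewed, and says that it supersedes the protocol's statistical sections. The SAP is therefore the text that must change; the protocol edit is for consistency.

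The cost is one phrase and one line of derivation code. Dates and times are already recorded for every infusion (protocol section 5.8). The clock time of AE onset is not mentioned explicitly, but the existing 24-hour window already requires it, so the change asks for no new kind of data. Before programming, confirm that the CRF holds infusion start and end times and AE onset time. If onset is recorded by date only, neither the present definition nor the corrected one can be derived exactly, and the SAP should state the rule for such cases.
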